5.3. Valid Diary

A valid diary record will not have more than 4 invalid entries (double or missed entries) over one 24-hour period. An invalid diary entry is defined as more than 1 entry recorded in a given half-hour interval, an unreadable entry, or the absence of an entry in a given half-hour interval.

5.4. Baseline for Diary Data

Baseline is defined as the average of the 3-day Baseline diary preceding the first dose.

5.5. Baseline Complete UPDRS Assessment

A valid UPDRS assessment is one in which UPDRS Part III has been completed in the ON state. The UPDRS assessment utilized as the baseline will be the later of the Screening or

Baseline visit assessment that is valid.

The selected assessment will be used to determine the Baseline UPDRS Parts I – IV subscores and the UPDRS I-IV total score. If a valid UPDRS is not available at Screening or Baseline visit, then the subject will be excluded from “change from baseline” UPDRS summary statistics.

5.6. Baseline for Blood Pressure and Pulse Rate and ECG

Baseline is defined as the average of the 3 pre-dose measurements for the respective supine or standing measurements that are taken following 5 minutes supine rest and following 3 minutes standing, respectively and approximately 10 minutes apart prior to the first dose of IMP. Should one of the 3 measurements be missing, the baseline will be the average of the remaining two pre-dose measurements and if two or more of the 3 measurements are missing, the average of the three measurements from the screening visit will be used as baseline. Should one of the 3 measurements be missing, the baseline will be the average of the remaining two screening measurements and if two or more of the 3 measurements are missing, baseline will be missing.

Baseline for ECG will be calculated similarly.

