6.2.2.1 Screening Assessments

1. Obtain written informed consent (see [Section 6.2.1](#)), and provide a copy to the patient.
2. Obtain demographics and previous medical history, including any co-existing pretreatment AEs.
3. Obtain neurological and PD history.
4. Obtain complete medication history including anti-PD medications (current and prior history). Record the date and approximate time of the most recent dose of levodopa taken prior to the Screening assessment.
5. Perform physical and neurological examination.
6. Obtain weight, height and calculate BMI.
7. Obtain and record serial BP and pulse measurements after at least 5 minutes supine rest and again after standing for approximately 1 and 3 minutes. Repeat these BP and pulse measurements 2 more times approximately 10 minutes apart.
8. Obtain 12-lead ECG. Ensure the ECG is collected when the patient is not experiencing dyskinesia that would interfere with an adequate recording.
9. Perform the following assessments in the ON state:
 - a. Perform full UPDRS Parts I, II, III (motor) and IV. UPDRS Part III should be performed approximately 1 to 3 hours after the patient has taken a scheduled dose of levodopa (preferably their morning dose of levodopa). UPDRS in the ON state will be measured at a time representative of the ON state in that patient, not in "best" ON.

- b. Modified Hoehn and Yahr stage in the ON state (estimate OFF state per history and document for entry criteria).
 - c. Administer the following assessment:
 - MMSE-II. (If the MMSE-II is not validated in the requisite language, the MMSE [Original] may be used.)
10. Administer the following assessments (may be done anytime during visit):
- a. C-SSRS.
 - b. Assessment for episodes of sudden onset of sleep.
 - c. mMIDI (Note: After Baseline, if patient has one or more positive modules on the mMIDI, their continued participation in the study should be discussed with the Medical Monitor).
11. For all applicable patients: Document method of contraception.
12. Obtain samples for the following laboratory tests and record the date and time of collection:
- a. For females who are postmenopausal for less than 2 years and who are not surgically sterile: obtain a blood sample for FSH.
 - b. For females of childbearing potential: urine pregnancy test.
 - c. Hematology and chemistry (including liver function tests).
 - d. TSH, free T3, free T4, and thyroperoxidase antibody.
 - e. Urine sample for urinalysis.

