AE, adverse event; BP, blood pressure; CGI-C, Clinical Global Impression of Change; C-SSRS, Columbia-Suicide Severity Rating Scale; d, day; ECG, electrocardiogram; eCRF, electronic case report form; ESS, Epworth Sleepiness Scale; ET, Early Termination; FSH, follicle stimulating hormone; IMP, investigational medicinal product; mMIDI, Modified Minnesota Impulse Disorders Interview; MMSE-II, Mini-Mental State Exam – Second Edition (MMSE-II); PD, Parkinson’s disease; PDQ-39, Parkinson’s Disease Quality of Life Questionnaire; PGI-C, Patient’s Global Impression of Change; UPDRS, Unified Parkinson’s Disease Rating Scale; V, Visit.

Footnotes

^a Screening period may not exceed 6 weeks.

^b Visit windows for scheduled visits after Baseline (V2) are in relation to the date of the Baseline Visit (V2).

^c Obtain and record BP and pulse measurements after at least 5 minutes supine rest and again after standing for approximately 1 minute and 3 minutes.

^d At Screening and Baseline (before dosing), obtain and record serial BP and pulse measurements after at least 5 minutes supine rest and again after standing for approximately 1 and 3 minutes, on 3 occasions approximately 10 minutes apart.

^e Optional activities (e.g., additional assessments for evaluation of AEs) that may be performed at the investigator’s discretion.

^f A resting supine 12-lead ECG will be collected after the patient has been in a supine position for a minimum of 5 minutes. Ensure the ECG is collected when the patient is not experiencing dyskinesia that would interfere with an adequate recording.

^g At Baseline, obtain three 12-lead ECGs (i.e., 3 serial readings, performed several minutes apart). Ensure the ECGs are collected when the patient is not experiencing dyskinesia that would interfere with an adequate recording.

^h To be collected during patient’s ON state.

ⁱ UPDRS to be measured in ON state. UPDRS Part III should be measured approximately 1 to 3 hours after patients have taken a scheduled dose of levodopa (preferably their morning dose of levodopa). Patients will be instructed to have already taken their normally scheduled dose of levodopa and their IMP before arriving at the study site in order to have their UPDRS Part III evaluated in the ON state. UPDRS in the ON state will be measured at a time representative of the ON state in that patient, not in the patient’s “best” ON.

Table 1: Schedule of Events/Evaluations (continued)

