5.7. Baseline for Variables excluding Diary Data, UPDRS, Blood Pressure, and Pulse Rate

Baseline is defined as the last measurement prior to the first dose of IMP. If for any parameter the study Day 1 pre-dose value is not done or missing, then the last value obtained at a Screening visit is used as Baseline.

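### The ECG baseline fallback in SAP 5.6 needs at least two Screening ECGs, but only one is scheduled, and SAP 5.7 leaves a conflicting rule in play

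*SAP*

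**What the plan says.** SAP 5.6 works in tiers. Baseline is the mean of three predose readings, or of two if one is missing. Below that, "if two or more of the 3 measurements are missing, the average of the three measurements from the screening visit will be used as baseline". The Screening tier repeats the pattern: two of the three Screening readings are enough, but "if two or more of the 3 measurements are missing, baseline will be missing". The rule is written for supine and standing blood pressure and pulse. ECG gets one sentence: "Baseline for ECG will be calculated similarly".

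The number of tracings is set elsewhere. Protocol 6.2.2.1, item 8, asks for one recording at Screening: "Obtain 12-lead ECG. Ensure the ECG is collected when the patient is not experiencing dyskinesia that would interfere with an adequate recording". Triplicate tracings belong to Visit 2 only. Footnote g of the schedule, which is attached to the Baseline column, reads "At Baseline, obtain three 12-lead ECGs (i.e., 3 serial readings, performed several minutes apart". Blood pressure and pulse differ, because footnote d asks for three sets at both Screening and Baseline.

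SAP 5.7 covers the remaining variables. Its heading excludes diary data, UPDRS, blood pressure and pulse rate, but not ECG. Its rule is "Baseline is defined as the last measurement prior to the first dose of IMP", with the last Screening value used if the predose value is missing. Protocol 11.3 has a similar general default, the last non-missing value before first dose, which gives way where something else is specified.

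**The concern.** A fallback designed for a measure taken three times at Screening has been extended to one taken once. A single tracing cannot meet a two-reading minimum, so the step meant to rescue a baseline leaves it missing. On the way, a lone valid Visit 2 tracing is set aside in favour of Screening data that cannot qualify.

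ECG is named in the primary objective. SAP 9.8.9 summarises change from baseline for each ECG parameter and counts patients by maximum QT/QTcF change, with cut-offs at 30 and 60 msec. A patient without a baseline cannot enter those tables, and SAP 9 states that missing data will not be imputed. Tracing loss is not far-fetched in this population: the protocol itself warns that dyskinesia can spoil a recording.

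Two sections of the SAP can also both be read as governing ECG, and they give different answers.

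**Working it through.** The plan gives no figure to reproduce here. The check is to run the rules on the scheduled tracings and then size the result.

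**Inputs.** Three ECGs at Visit 2 (schedule footnote g), one at Screening (Protocol 6.2.2.1, item 8), a two-reading minimum in each tier (SAP 5.6), and 450 patients planned (SAP 3.2).

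**Step 1: every combination of valid tracings.**

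| Valid Visit 2 ECGs | Screening ECG | SAP 5.6, read literally | SAP 5.7 |
|---|---|---|---|
| 3 | 0 or 1 | mean of 3 | last predose |
| 2 | 0 or 1 | mean of 2 | last predose |
| 1 | 1 | missing | last predose |
| 1 | 0 | missing | last predose |
| 0 | 1 | missing | Screening value |
| 0 | 0 | missing | missing |

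All four combinations that reach the 5.6 fallback return missing, and in three of them a pretreatment ECG exists. For blood pressure and pulse, with three Screening sets scheduled, the same fallback works whenever two or three sets are present. The two sections also differ when nothing is missing: 5.6 takes a mean, 5.7 the last reading.

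**Step 2: size.** The documents give no rate of missing ECGs. Let m be an assumed probability that any one Visit 2 tracing is missing, independently of the others. Then

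P(two or more of three missing) = 3m²(1 − m) + m³.

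| m (assumed) | Calculation | Probability | × 450 |
|---|---|---|---|
| 1% | 0.000297 + 0.000001 | 0.000298 | 0.13 |
| 2% | 0.001176 + 0.000008 | 0.001184 | 0.53 |
| 5% | 0.007125 + 0.000125 | 0.00725 | 3.3 |
| 10% | 0.027 + 0.001 | 0.028 | 12.6 |

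The first term is the chance of exactly one valid predose tracing. Times 450, it gives 0.13, 0.53, 3.2 and 12.2.

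**Step 3: dependence.** Serial tracings at one visit are unlikely to fail independently, since equipment failure or dyskinesia could affect all three. If the three were always lost together, the probability would be m itself. At 5% that is 450 × 0.05 = 22.5 patients, all with no Visit 2 tracing. Clustering can therefore raise the count for a given m, and it moves cases from one valid predose tracing to none.

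**The case against.** The strongest reply is that the word used for ECG means alike, not identical. The blood pressure text cannot be carried over word for word anyway: it speaks of standing readings and a ten-minute spacing, neither of which applies to a supine ECG repeated several minutes apart. A programmer has to adapt it, and using the one Screening ECG is a natural adaptation. This stands in part. A reader might infer that the fallback is bound to return missing, but that follows only under a literal reading and with no unplanned repeat ECG at Screening. The documents schedule no repeat and do not describe the adaptation, so the choice is left open.

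Second, the trigger should be uncommon. Exclusion criterion 5 (Protocol 4.2) needs the average QTcF from three Baseline ECGs. Protocol 6.2.3.1 assigns IMP only after eligibility is confirmed and predosing procedures are done. Protocol 9.4.2 has eligibility judged on the machine printout. A treated patient with fewer than two valid tracings would generally reflect a deviation or a tracing lost later, for example at central overread. This stands and favours the low end of the range, though it does not make the count zero.

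Third, a two-reading minimum may be deliberate, because a baseline from one tracing is noisier and can itself disturb the >60 msec count. That is a fair reason to flag such patients. It does not explain a Screening tier that the schedule cannot satisfy.

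Finally, if 5.7 governs, any patient with a predose or Screening ECG keeps a baseline. But 5.6 names ECG and is the more specific rule, so the conflict makes the loss uncertain without settling which section applies.

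**Conclusion.** The concern holds as a mismatch between a stated rule and the schedule. On the scheduled procedures and a literal reading of SAP 5.6, the ECG fallback cannot produce a baseline, and 5.7 arguably supplies a conflicting one. Patients with fewer than two valid Visit 2 ECGs would leave the ECG change-from-baseline summaries, including the >30 and >60 msec categories.

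The effect is probably small: about 0.1, 0.5, 3 or 13 of 450 patients at assumed independent per-tracing rates of 1%, 2%, 5% or 10%. Those rates are not in the documents, and clustered loss would change the counts.

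Two stronger readings are not supported. A reader might infer that nearly all affected patients have a valid predose tracing that is discarded, but that follows from the independence assumption. A reader might also infer that the QTcF evaluation as a whole is compromised. Observed values, the maximum QT/QTcF categories including >500 msec, clinically significant findings and listings do not use this baseline. The study is single-arm and descriptive, with no tests, so no treatment comparison is altered. This is a worthwhile clarification, not a serious flaw.

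**What to change.** Give ECG its own rule in SAP 5.6: baseline is the mean of the available Visit 2 predose ECGs (one, two or three), and if there are none, the single Screening ECG. Add ECG to the variables excluded in the 5.7 heading. Baseline would then be missing only when no Visit 2 or Screening ECG exists, and the three patterns now lost despite a pretreatment tracing would be kept.

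The cost is two SAP sentences, using data already collected. The drawback is the noisier single-tracing baseline, so flag or footnote those patients in the change-from-baseline tables. The change concerns the analysis baseline only and leaves the QTcF withdrawal criterion in Protocol 4.3.2 untouched.

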5.7. Baseline for Variables excluding Diary Data, UPDRS, Blood Pressure, and Pulse Rate

Baseline is defined as the last measurement prior to the first dose of IMP. If for any parameter the study Day 1 pre-dose value is not done or missing, then the last value obtained at a Screening visit is used as Baseline.

5.8. Change from Baseline

Change from baseline will be calculated as the data value measured post-baseline visits minus baseline.

5.9. Concomitant and Prior Medication other than Anti-PD Medications

Concomitant medications other than anti-PD medications are defined as any medications ongoing at the start of treatment or with a start date and time on or after the date of first dose of IMP. Prior medications are defined as a medication with a stop date prior to first dose of IMP.

For the classification of medications as prior or concomitant, medications with missing or partial stop dates will be considered as follows:

- If the stop date is completely missing, the medication will be regarded as concomitant.
- If the day and month are missing but the year is given and the year is prior to the year of first dose, the medication will be classified as prior medication. Otherwise such medications will be considered as concomitant.
- If the day is missing but the month and year are given and the month and year are prior to the day of first dose, the medication will be classified as prior medication. Otherwise such medications will be considered as concomitant.

5.10. Concomitant Anti-PD Medications

During the study, patients' concomitant anti-PD medications may be adjusted as needed under the investigator's supervision.

Concomitant anti-PD medications are defined as any medications ongoing at the start of treatment or with a start date and time on or after the date of first dose of IMP. Prior anti-PD medications are defined as a medication with a stop date prior to first dose of IMP.

For the classification of anti-PD medications as prior or concomitant, medications with missing or partial stop dates will be considered as follows:

- If the stop date is completely missing, the medication will be regarded as concomitant.
- If the day and month are missing but the year is given and the year is prior to the year of first dose, the medication will be classified as prior medication. Otherwise such medications will be considered as concomitant.
- If the day is missing but the month and year are given and the month and year are prior to the day of first dose, the medication will be classified as prior medication. Otherwise such medications will be considered as concomitant.

5.10.1. Baseline Total Daily Levodopa

The total daily levodopa dose at baseline will be calculated as dose x # of tablets x frequency per day for levodopa medications taken at baseline.

5.10.2. Baseline Total Daily Levodopa Equivalents

The Levodopa Equivalents (LED) of each concomitant anti-PD drug being taken at baseline will be calculated as the total daily dose of the medication multiplied by a conversion factor to obtain the LED for the medication. The total daily LED will be the sum of each LED medication taken at baseline. Conversion factors for each medication will be based on Tomlinson et al, 2010 (see [Section 12](#)). Algorithm based on the Tomlinson paper is included in [Appendix 2](#).

5.11. Missing Adverse Event Relationship or Severity

AEs with missing relationship will be considered as having a relationship of possibly related to study drug. AEs with missing or unknown severity will be considered severe. A subject with missing relationship or severity for an AE will be footnoted as having missing data in the corresponding tables and listings for the AE with missing data.

5.12. Treatment-Emergent Adverse Events (TEAEs)

TEAEs are AEs which first occur or increase in severity or relationship to study drug after the first dose of IMP through the Safety Follow-up. Should the day of the AE be “unknown” and the AE in question occurs in the same month or a following month as the date of first dose, the AE will be considered treatment emergent. Should the month of the AE be “unknown” and the AE in question occurs in the same year or a following year as the date of first dose, the AE will be considered treatment emergent. Should the start date be missing then the AE will be considered treatment emergent.

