6.2.3.4 Assignment and Dispensing of Investigational Medicinal Product

Note: Sites participating in Expanded PK Sampling should refer to [Appendix 15.9.1](#) for Assignment and Dispensing of IMP instructions.

1. For patients meeting all entry criteria, complete the IMP assignment transaction using the IXRS by following the procedures provided.
 - a. Dispense the open-label IMP bottle(s) assigned by the IXRS to the patient for this study visit. Each bottle consists of either 50 tablets of 120 mg tozadenant or 100 tablets of 60 mg tozadenant.
 - b. Record the date IMP was dispensed in IMP dispensing records including patient number, assigned IMP bottle number(s), and date and time IMP was dispensed.
 - c. Review the dosing instructions for the IMP with the patient, answer any questions, and remind the patient to return the IMP (including all used, unused and partially used bottles) at the next visit.
 - d. Patients will be instructed to take either two (2) 60 mg tablets or one (1) 120 mg tablet of the dispensed IMP by mouth BID, in the morning and in the evening preferably at the same time each day, for a total of either two (2) 120 mg tablets or four (4) 60 mg tablets per day. The evening dose should be approximately 12 hours after the morning dose. Patients will be instructed to take their morning and evening doses 1 hour before or 2 hours after a meal and to refrain from eating for 1 hour after dosing. Patients should take the first dose of IMP at home after the Baseline Visit.
2. Instruct the patient to take the first dose of IMP at home on the evening of dispensation.
3. Ensure that the patient understood the dosing instructions and the use of the extra doses included in the bottle if visit delayed and/or use of visit window.
4. Schedule the Week 2 visit. If needed, use the visit window in relation to the date of the Baseline visit.

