9.0 ASSESSMENT OF SAFETY

9.1 Adverse Events

9.1.1 Definition of Adverse Event

An AE is any untoward medical occurrence in a patient or clinical investigation patient administered a pharmaceutical product that does not necessarily have a causal relationship with this treatment. An AE can therefore be any unfavorable and unintended sign (including an abnormal laboratory finding), symptom, or disease temporally associated with the use of a medicinal (investigational) product, whether or not related to the medicinal (investigational) product.

In order to ensure complete safety data collection, all AEs occurring during the study (i.e., after the signing of the ICF), including any pretreatment and post-treatment periods required by the protocol, must be recorded in source documents and the eCRF even if no investigational product was taken but specific study procedures were conducted. This includes all AEs not present prior to the initial Screening Visit and all AEs that recurred or worsened after the initial Screening Visit. Events that occur prior to dosing are captured as medical history and pretreatment AEs. Events that occur after Baseline and prior to dosing are captured as AEs.

Signs or symptoms of the condition/disease for which the investigational product is being studied should be recorded as AEs only if their nature changes considerably or their frequency or intensity increases in a clinically significant manner as compared to the clinical profile known to the investigator from the patient's history or during the baseline period.

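### SAP 5.12 counts an adverse event with an incomplete onset date as treatment-emergent even when its stop date falls before the first dose

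*SAP*

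**What the plan says.** SAP 5.12 opens with a definition based on timing: "TEAEs are AEs which first occur or increase in severity or relationship to study drug after the first dose of IMP", up to the Safety Follow-Up. It then gives three defaults for incomplete onset dates.

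- Day unknown: if "the AE in question occurs in the same month or a following month as the date of first dose, the AE will be considered" treatment-emergent.
- Month unknown: the same result if "the AE in question occurs in the same year or a following year as the date of first dose".
- No date at all: "Should the start date be missing then the AE will be considered treatment emergent".

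None of the three depends on the stop date, the visit at which the event was reported, or the type of record. SAP 9.8.1 and 9.8.2, which describe the AE tables, add no exception.

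The protocol ensures that events from before dosing are collected. Section 9.1.1 requires recording of "all AEs occurring during the study (i.e., after the signing of the ICF), including any pretreatment and post-treatment periods required by the protocol". It adds that "Events that occur prior to dosing are captured as medical history and pretreatment AEs", and footnote n of the Schedule of Events labels AEs at Screening and Baseline as pretreatment. The next sentence of 9.1.1 is narrower: "Events that occur after Baseline and prior to dosing are captured as AEs". Section 6.2.3.4 places the first dose after the visit: "Instruct the patient to take the first dose of IMP at home on the evening of dispensation".

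**The concern.** Counting an event as treatment-emergent when its timing cannot be determined is a sensible default. The difficulty is that this default also applies when the timing can be determined. An event with a known stop date before the first dose cannot have begun after it, however little is known about its start. Under 5.12 it still becomes a TEAE whenever the known part of the onset date falls in the first-dose month or year, or there is no onset date.

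Protocol 11.5 names the occurrence of TEAEs as the primary safety variable. All patients share one treatment label (SAP 5.1), so there is no comparator rate against which a surplus would show. The error runs one way. It could also put a preferred term in the TEAE table that no patient experienced after dosing.

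**Working it through.** The plan gives no figure for this rule, so there is nothing to reproduce. The check has three parts.

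**1. The rule applied literally.** Take an example first dose on 20 June 2017 and, in the first three rows, an AE that stopped on 10 June 2017.

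| Onset as recorded | Default in 5.12 | Result of the default | Opening definition in 5.12 |
|---|---|---|---|
| Day unknown, June 2017 | Same month as first dose | TEAE | Not a TEAE: ended before dosing |
| Day and month unknown, 2017 | Same year as first dose | TEAE | Not a TEAE: ended before dosing |
| Missing | Missing start date | TEAE | Not a TEAE: ended before dosing |
| Day unknown, May 2017 | Earlier month | Not a TEAE | Not a TEAE unless it later increased |

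In the first three rows the default and the opening definition disagree. With a stop-date override all three become not treatment-emergent. An event that stopped on or after the day of first dose, or has no stop date, is unaffected by that override.

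**2. How far the default reaches among pre-dose events.** Inputs: a Screening Period of 1 to 6 weeks, that is 7 to 42 days (Protocol 3.1.1). Assumptions, not in the documents: onset uniform over the screening window, and first dose uniform over a 365-day year.

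For an onset j days before the first dose, the chance that both fall in the same month is 1 − 12j/365 for j up to 28. The chance that both fall in the same year is 1 − j/365. Averaging over j = 1 to L uses a mean j of (L + 1)/2:

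- L = 7: month 1 − 12 × 4/365 = 0.868; year 1 − 4/365 = 0.989
- L = 14: month 1 − 12 × 7.5/365 = 0.753; year 1 − 7.5/365 = 0.979
- L = 28: month 1 − 12 × 14.5/365 = 0.523; year 1 − 14.5/365 = 0.960
- L = 42: month 0.350, by enumeration over the calendar because lags beyond a month contribute nothing; year 1 − 21.5/365 = 0.941

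So about 35% to 87% of pre-dose AEs with an unknown onset day fall under the same-month default, 94% to 99% of those with an unknown month fall under the same-year default, and all of those with no start date become TEAEs. These shares apply only to pre-dose AEs whose onset date is already incomplete. The stop-date override would correct those among them that also ended before dosing.

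**3. Size per patient.** Planned enrolment is 450 (Protocol 3.1.2). Patients count once within each preferred term, so one affected patient adds at most 1/450 = 0.0022, or 0.22 percentage points, to a row. The addition is nil if that patient has a genuine TEAE with the same term, and a little larger if fewer than 450 are dosed.

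**Are the data available?** SAP 9.8.1 lists AE duration and Protocol 9.1.5 refers to the end date of a pretreatment event, so stop dates should be held. SAP 9.8.1 also includes non-treatment-emergent events in the eCRF AE listing, so the SAP does not place pre-dose events outside the AE data to which the date rule applies.

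**The case against.** The best defence is that the defaults are subordinate to the opening definition, that pre-dose events are captured as medical history or pretreatment AEs and may be set aside before the date rule is reached, and that 5.12 follows the worst-case approach of SAP 5.11, where missing severity becomes severe and missing relationship becomes possibly related. Data queries should also leave few incomplete dates.

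Part of this stands. The default is right for onsets that are truly ambiguous, and few records are likely to be affected. But the SAP nowhere says that pretreatment records are filtered out. Record type would not be sufficient either, because Protocol 9.1.1 enters events between Baseline and dosing simply as AEs, though that gap should last only hours. A programmer following 5.12 as written would produce the results in the table.

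Four stronger readings are tempting and not supported:

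- *That such events are attributed to tozadenant.* Treatment-emergent is a label of timing. SAP 9.8.1 tabulates related TEAEs separately, and a pre-dose event would enter that table only if rated possible or probable, or if its relationship were missing.
- *That 35% to 87% measures how common the error is.* It is conditional on a pre-dose AE with an unknown onset day; the documents give no frequency for these.
- *That 5.12 conflicts with SAP 5.9 and 5.10, which use stop dates for medications.* Prior medication is defined by its stop date, whereas a TEAE is defined by onset or increase. Those sections offer usable partial-date logic, but do not create an inconsistency.
- *That an increase in relationship to study drug should be removed as a trigger.* A causality rating may rise because of the event's course after dosing, so keeping the trigger is a defensible choice.

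**Conclusion.** The point holds as a minor gap in a stated rule. For AEs with a partial onset date in the first-dose month or year, or with none, 5.12 gives a result contrary to its own definition when the stop date precedes the first dose. The effect is upward only, at most 0.22 percentage points per affected patient in a preferred-term row at 450 patients, and the number of such patients cannot be obtained from the documents. It is probably very small, since it requires a pre-dose AE, an incomplete onset date, and evidence that the event preceded dosing. The conclusion rests on reading 5.12 literally and on stop dates being in the database. It does not put the overall safety description in doubt.

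**What to change.** Add one sentence to SAP 5.12: *An AE with a partial or missing onset date that meets one of the defaults above is treated as treatment-emergent unless (a) its stop date, or the known part of it, shows that it ended before the first dose of IMP, or (b) where the eCRF identifies it, it was recorded as a pretreatment AE at or before the Baseline Visit and did not worsen after dosing.*

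The override switches off only the date default. An event that meets the opening definition through a later increase still counts, and Protocol 9.1.5 already has a worsened pretreatment event reported again with its own start date.

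The cost is a sentence and a programming condition. Limb (a) should need no new data. Limb (b) depends on an eCRF field that cannot be confirmed from these documents, so it is worded conditionally. The downside is a slightly less conservative TEAE count; because all AEs are listed in any case, reclassified events stay visible.
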